**9) Data and/or Specimen Banking**

N/A

**10) Provisions to Monitor the Data to Ensure the Safety of Subjects**

There is potential minimal risk. There is potential loss of confidentiality; however, for all data, only study personnel will have access to these materials. Although the research coordinator will view identifiable information from the health records, the data downloaded from REDCap to be used for analysis will all be de-identified. All data will be destroyed 7 years after completion of the study.

There is no risk to data security with regards to letting the parents use their personal device/computer to conduct virtual FCR, because the telehealth connection requires the download and use of the HIPAA-compliant application, Extended Care. This telehealth application platform to be used will be a secure platform that meets HIPAA and HITECH data security requirements. Therefore, since the telehealth intervention in this pilot trial will use a secure telehealth application to conduct virtual FCR, the communication will be secure. In this study, virtual FCR will only proceed using the HIPAA compliant application, since the videoconference connection is established through the HIPAA compliant application. No aspects of the virtual FCR encounter will be recorded nor stored in any way.

There are no anticipated risks to patients with regards to assignment to the intervention (virtual FCR). The intervention places no pressure on clinicians to alter clinical management. Rather, the intervention assigns the use of telehealth as an additional mode of communication to enhance the in person standards of FCR.

The alternative to virtual FCR is standard in person FCR or to not attend rounds at all. The benefits of in person FCR are not needing to communicate using a technology interface. However, the risks of in person FCR include the inability of the family to be able to physically be in the NICU during rounds, and thus to participate in FCR at all.

For the qualitative interview participants, there is potential minimal risk. Parents (or clinicians) might experience distress discussing their experiences during the NICU hospitalization of their child. However, this research team has previously conducted qualitative interviews with NICU parents who were asked to

**PROTOCOL TITLE: Virtual Family-Centered Rounds in the Neonatal Intensive Care Unit:  
A Randomized Clinical Trial**

reflect on their experiences when their child was hospitalized. In these interviews, informants did not report or demonstrate any distress. It is thus unlikely that such distress will occur with the proposed study. There exists a minimal risk of loss of confidentiality.

**11) Withdrawal of Subjects**

Subjects will only be withdrawn if they no longer meet inclusion criteria. For example, this might occur if a neonate (subject) is enrolled but then has a CPS placement of visitor restrictions. At that point, we will inform the recruited parents, if applicable, that they no longer meet criteria to participate in the trial. This circumstance would be no different than their routine care, since a CPS restriction would prohibit them from joining FCR; so we would similarly restrict them from joining virtual FCR.

Families randomized to use the intervention can choose to use or not use the intervention as they see fit, and it will not impact their participation in the study. Families will be free to choose to complete or not complete the surveys the week of discharge.

**12) Risks to Subjects**

There is potential loss of confidentiality; however, for all data, only study personnel will have access to these materials. Although the research coordinator will view identifiable information from the health records, the data downloaded from REDCap to be used for analysis will all be de-identified. All data will be destroyed 7 years after completion of the study

**13) Potential Benefits to Subjects**

It is possible that families who have the intervention available to them find benefit in being able to participate in family-centered rounds while not being present in the NICU.

**14) Multi-Site Research**

N/A

**15) Community-Based Participatory Research**

N/A

**16) Sharing of Results with Subjects**

Results will not be shared with subjects. Summary of findings will be reported in the form of manuscripts and presentations at scientific meetings.

## 17) Prior Approvals

N/A

## 18) Provisions to Protect the Privacy Interests of Subjects

All information will be kept in secure REDCap or Excel databases and the only link between the patient and the REDCap will be a Study ID. We will use a "Participant Log" excel file to store data that links the Study ID with the subject. This log will include the following information: Study ID, patient name, MRN, CSN, intervention vs. control arm, admit date, enrolled date, parent identify (e.g., "mom"), parent cell/email preferred contact, subscription status, and disposition. This "Participant Log" will be stored on the secure UC Davis server.

Families will be free to use the intervention if/when it works for them. Families randomized to the intervention can opt out of using it entirely, with no penalty to them or their child. Families are free to answer (or not answer) the surveys the week of discharge and at 30, 60, and 90 days after discharge, with no penalty to them or their child.

Only members of the research team will have access to the data.

## 19) Compensation for Research-Related Injury

N/A

## 20) Economic Burden to Subjects

N/A

## 21) Drugs or Devices

N/A

## 22) Review Requirements

**Are there any contractual obligations or other considerations that require IRB review of this research, or review at intervals other than those required by the Common Rule or FDA? If yes, check box:**

Yes

**✗** No

## STATISTICAL ANALYSIS PLAN

### Statistical methods for primary and secondary outcomes

Our primary analysis strategy will analyze all available data from participating family units and their members, with groups defined according to the randomized assignment (intervention versus control) for that family unit. We will use graphical and analytical descriptive statistics to summarize infant, parent, and family unit characteristics. We will use methods for clustered survey data to adjust confidence intervals for family units with multiple parental respondents. We will not use cluster-adjusted confidence intervals for family units with multiple infants unless the mean number of infants per family unit unexpectedly exceeds 1.10.

We will use generalized linear models to estimate intervention effect sizes and confidence intervals and to test hypotheses for outcomes. Independent variables will include a binary indicator for intervention assignment along with a parsimonious set of subject characteristics as covariates (parent age, race, ethnicity, gender, education, transportation security, marital status, other children dependents, digital literacy score). We will specify the generalized linear mixed models as linear, logistic, or Poisson regressions, according to the outcome type. Random effects will be specified to accommodate the multilevel structure of the data and the nesting of longitudinal measurements, when applicable, within parents and the nesting of parents and infants within family units.

To account for increased exposure among subjects with longer neonatal intensive care unit (NICU) stays when analyzing the primary outcome, we will use Poisson regression to compare rates for the family-centered rounds (FCR) parent attendance outcome between intervention vs. control group subjects, using the numerator for this outcome as the dependent variable and using the logarithm of the denominator as an offset term. We will also use Poisson

regression for analyzing the error rate outcomes, with the offset being the logarithm of the number of days in the NICU. The exponentiation of the Poisson regression coefficient for the treatment indicator will thus represent an adjusted between-arm rate ratio for FCR parent attendance.

For parent experience and family-centered care, we will use the top-box scoring method and assess intervention effects on the individual items as well as on the summary scores. For parent health-related quality of life (HRQOL), we will similarly assess the intervention effects on the PedsQL™ Family Impact Module 36 items, eight subscales, and summary scores (overall total score, Parent HRQOL Summary score, and Family Functioning Summary score). To accommodate the longitudinal data collection for the HRQOL outcomes, we will use generalized linear mixed models that include main effects for time, study arm, and the interaction, to estimate timepoint-specific intervention effects. We will also evaluate the effect of the intervention on the remaining outcomes.

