#### **4) Inclusion and Exclusion Criteria**

This study is a randomized trial to compare virtual family-centered rounds (**FCR**) to standard FCR for neonatal intensive care unit (**NICU**) patients. We will simultaneously conduct an intervention evaluation of this virtual FCR intervention. The unit of randomization is at the subject level (the neonate). The site is the UC Davis NICU. To gather necessary data on efficacy outcomes and on the 5 dimensions for the intervention evaluation (Reach, Effectiveness, Adoption, Implementation, Maintenance), survey data will be collected from the subjects’ parent or guardian (referred to as “parent” hereafter), electronic health record (EHR) data will be collected from UC Davis, and daily weekday FCR observations will be performed. To gather necessary data for the intervention evaluation, qualitative interviews will be performed.

- INCLUSION: (NEONATES) Neonates aged <365 days admitted to UC Davis neonatal intensive care unit (NICU) during the study period who have one or more parent or guardian that self-reports their preferred language to be English. This parent must also be non-incarcerated and aged  $\geq 18$  years.
- EXCLUSION: (NEONATES) Age > or = 365 days. Neonates with visitation or information restrictions placed by child protective services. Neonates with more than one admission during the trial period will be included only on their first admission.
- INCLUSION: (QUALITATIVE INTERVIEWS) Parents/guardians of the eligible patients (described above) and NICU clinicians (e.g., nurses, physicians). Age 18 years and older.
- EXCLUSION: (QUALITATIVE INTERVIEWS) Age less than 18 years. Non-English speaking.
- INCLUSION: (SURVEY) Parents/guardians of the eligible patients (described above). Age 18 years and older.

**PROTOCOL TITLE: Virtual Family-Centered Rounds in the Neonatal Intensive Care Unit:  
A Randomized Clinical Trial**

- EXCLUSION: (SURVEY) Age less than 18 years. Non-English speaking.

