**ASSIGNMENT TO CONTROL VERSUS INTERVENTION:** The unit of randomization is at the subject (neonate) level. The study statistician will generate a random allocation list and employ allocation concealment to assign eligible subjects with a 2:1 intervention-to-control arm ratio. During the 12-month enrollment (intervention delivery) period, a research coordinator will open the sequentially numbered assignments to invite parents of neonates assigned to the intervention arm to sign up for virtual FCR. Neonates of parents accepting this offer will be considered “subscribed.” For neonates with more than one eligible parent, separate subscription invitations will be used for each parent.

**DELIVERY OF INTERVENTION:** We will use Extended Care as the software interface for virtual FCR. This secure platform meets HIPAA security rules and launches from the electronic health record. Parents will use the Extended Care application on their personal computer or smart device. The NICU medical team will use Extended Care on a computer on wheels with a speaker and camera. Virtual FCR will be available for parents of subscribed neonates to attend Monday through Friday. For neonates with a subscribed parent, a NICU team member will launch an ExtendedCare telehealth visit (“virtual room”) from the patient’s Epic chart. From ExtendedCare, a NICU team member will use the “invite” feature to invite the subscribed parent(s); the parents then receive a message to their email/cell phone that includes their child’s unique Extended Care link. The parent(s) can use this link, if desired, to enter the “virtual room.” If a parent joins, they will establish the live, bidirectional audio and visual connection. FCR will then proceed in usual fashion. Parents can participate in virtual FCR as much, or as little, as they choose. They can also participate in FCR in person (standard of care) or not participate at all.

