the time of [i.e., 2 days before the anticipated] discharge. If a neonate has two eligible parents, separate invitations will be sent to each parent. Recruitment will occur via giving them a packet at discharge. The packet will contain a recruitment letter (flyer), a scannable barcode (to access the survey electronically if preferred), a website link (another alternative to access the survey electronically if preferred), and a paper version of the survey. Alternatively, since parents are not often at the bedside for in-person recruitment, the research assistant will send a secure message/email from StudyPages or make a phone call to invite participants to participate in an interview. Parents can complete the survey themselves or verbally with the research assistant who will directly input verbal responses into REDCap. The research assistant will make 3 daily attempts of outreach and follow up with non-respondents 7 days later. If a survey is not returned within 21 days of discharge, the survey will be considered a non-response. The survey delivery process from a Secure Chat message/email or phone call will occur at 30, 60, and 90 days to administer the subsequent survey packets (with 3 daily attempts and follow-up 7 days later and a 21-day response time limit). Electronic surveys will be conducted in REDCap. Paper surveys will be kept in a locked box in the locked physician workroom until collected by a research assistant, who will transfer the data into REDCap and then destroy the paper copy. For parents with more than one neonate enrolled in the study (i.e., twins/multiples), the parents will only receive one survey packet per child. The survey will be sent to the parents at the time that one of their children first discharges from the NICU (and each subsequent 30 day period will be based off that first child's discharge date). For subsequent siblings discharged at later dates, a research assistant will use StudyPages to message/call parents to obtain the responses to (a) questions #1 and 2 of the 30-day survey and (b) question #1 of the 90-day survey. These questions relate to the outcomes of (a) 30-day revisit/readmission and (b) 90-day breastmilk feeding. The research assistant will directly input the responses into REDCap.

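### The protocol randomises neonates, the SAP groups by family unit, and the SAP gives two conflicting rules for sibling clustering

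*Combined protocol and SAP*

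**What the plan says.** **Unit of assignment.** Protocol section 7 (assignment to control versus intervention) states: "The unit of randomization is at the subject (neonate) level". Section 4 says the same. The survey procedures in section 7 provide for parents with twins or other multiples in the trial, so siblings can both be enrolled. The SAP (statistical methods for primary and secondary outcomes) analyses family units and their members, "with groups defined according to the randomized assignment (intervention versus control) for that family unit". Nothing in the documents says how a second sibling is allocated.

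**Clustering.** The same SAP section adjusts intervals for families with more than one parent respondent. For infants it then says: "We will not use cluster-adjusted confidence intervals for family units with multiple infants unless the mean number of infants per family unit" turns out, contrary to expectation, to be above 1.10. The next paragraph specifies random effects to accommodate, among other things, "the nesting of parents and infants within family units", with no threshold.

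**Outcomes affected.** For the primary outcome, "we will use Poisson regression to compare rates for the family-centered rounds (FCR) parent attendance outcome", with the log of the number of rounds as offset. The sample size (protocol section 8) rests on length of stay: 447 neonates randomised and 429 analysed, giving 80% power.

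**Parent surveys.** Section 7 says "the parents will only receive one survey packet per child". It then times the survey from the first sibling's discharge and asks only selected questions for later siblings.

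**The concern.** A family has a single randomised assignment only if all its enrolled infants are in the same arm. The SAP takes this for granted, but the protocol's randomisation text does not provide it. The two possible practices have different consequences.

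- **Siblings share an arm.** Their outcomes are correlated and carry the same treatment, so an analysis that treats them as independent understates the variance. This bears on length of stay and on the primary outcome, because the same parents attend rounds for both infants. The 80% power also assumes 429 independent neonates.
- **Siblings are randomised separately.** Intervals are then not too narrow on this account, but some families straddle both arms. They have no family assignment, a parent may be invited to virtual rounds for one infant and not the other, and shared parent-reported outcomes have no stated arm.

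The two clustering rules disagree whenever the mean is 1.10 or less, which is the case the SAP expects. A family random effect is itself a cluster adjustment of the interval. Two analysts could therefore follow this SAP faithfully and report different intervals for the primary outcome.

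**Working it through.** **Inputs from the documents.** Protocol section 8: SD of log length of stay 1.0 (mean 3.0), 25% reduction in geometric mean, two-sided alpha 5%, power 80%, 4% attrition, 298 and 149 randomised (2:1). SAP: threshold 1.10.

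**Assumptions, because the documents give no figure.** Families have one or two infants; the mean per family is 1.05 or 1.10 (the most the rule tolerates without adjustment); the sibling ICC after covariates is 0.3, 0.5 or 1 (upper bound).

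**Step 1: the plan's own figure.** The effect is |ln 0.75| = 0.2877. The control-arm size is (1.960 + 0.842)² × 1.0² × (1 + 1/2) / 0.2877², which rounds up to 143. The total is 3 × 143 = 429, and 429/0.96 rounds up to 447. Both figures reproduce. Power with 286 and 143 is 80.0% (t-test), with no allowance for siblings.

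**Step 2: design effect with siblings in the same arm.** DEFF = 1 + (E[m²]/E[m] − 1) × ICC, where m is the number of infants per family.

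- Mean 1.05: (0.95 + 4 × 0.05)/1.05 − 1 = 0.0952.
- Mean 1.10: (0.90 + 4 × 0.10)/1.10 − 1 = 0.1818.

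**Step 3: consequences for length of stay.** The true alpha of an unadjusted test is 2 × (1 − Φ(1.96/√DEFF)). Adjusted power is the two-sample t-test with the variance multiplied by DEFF. Interval widening is √DEFF − 1.

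| Mean | ICC | DEFF | True alpha, unadjusted | Power, unadjusted | Power, adjusted |
|---|---|---|---|---|---|
| 1.05 | 0.3 | 1.029 | 5.3% | 79.9% | 78.9% |
| 1.05 | 0.5 | 1.048 | 5.5% | 79.7% | 78.2% |
| 1.05 | 1 | 1.095 | 6.1% | 79.1% | 76.4% |
| 1.10 | 0.3 | 1.055 | 5.6% | 79.6% | 77.9% |
| 1.10 | 0.5 | 1.091 | 6.1% | 79.2% | 76.5% |
| 1.10 | 1 | 1.182 | 7.1% | 78.3% | 73.2% |

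Nominal 95% intervals cover 94.7% down to 92.9%. The unadjusted test keeps its power only at the inflated alpha. Adjusted intervals are wider by 1.4% (DEFF 1.029) to 8.7% (DEFF 1.182).

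Simulation (20,000 trials per case, 429 neonates, family-level assignment) agrees: unadjusted alpha 5.6% to 7.5%, family-robust alpha 5.0% to 5.5%, family-robust power 79.1% to 73.4%.

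**Step 4: attendance.** I ran 10,000 null simulations in each of 16 cases. Log length of stay was 3.0 ± 1.0, with rounds on 5 of 7 days. Assumed values were attendance of 30% or 50% at the average infant, between-infant logit SD 1.0 or 1.5, sibling length-of-stay correlation 0.5, and attendance ICC 0.5 or 1.

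- Poisson rate ratio with infant-robust errors: alpha 6.1% to 7.7%.
- With family-robust errors: 5.6% to 6.6%.
- Case by case, ignoring the family adds 0.2 to 1.4 percentage points; a repeat simulation gave up to about 1.7.
- Clustering siblings raises the variance by 2% to 10%, so intervals widen by about 1% (√1.02 − 1) to 5% (√1.10 − 1).

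**Step 5: siblings randomised separately, only if that happens.** The chance that a twin pair splits at 2:1 is 2 × 2/3 × 1/3 = 44%. At a mean of 1.05, 447/1.05 ≈ 426 families, 21 pairs and about 9 split. At 1.10, 447/1.10 ≈ 406 families, 41 pairs and about 18 split.

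**The case against.** **The rules might be reconciled.** The 1.10 sentence follows one about methods for clustered survey data, so it could limit only that correction while the mixed models handle siblings. Or the specific threshold could govern the general random-effects sentence. Either is possible, but the SAP states neither, and they lead to opposite analyses.

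**The rule is prespecified and the effect is small.** The authors expect a mean below 1.10. At 1.05 with an ICC of 0.3 to 0.5, alpha is only 5.3% to 5.5%. This stands as a statement about size. It does not justify the rule: the bias depends on the ICC as well as on family size, the SAP gives no reason for 1.10, and adjustment costs almost nothing.

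**The power figures mix a residual ICC with the raw SD.** This is fair. If covariates explained about 4.6% of the variance (1 − 1/1.048), they would offset a DEFF of 1.048; about 15% would offset 1.182. The documents give no such figure, so the power shortfalls are illustrative. Alpha and coverage depend only on DEFF and are not affected.

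**The attendance simulation is not exactly the SAP's model.** Also fair: its inputs are assumed, and an ICC of 0.3 was not tried. Family-robust errors do not bring alpha back to 5% either, because long stays dominate the total, which is a separate matter. The simulation shows only the increment from ignoring siblings.

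**Split twins are hypothetical.** The SAP's wording points to shared assignment, and no section confirms separate randomisation. The protocol's wording nevertheless permits it, so the rule has to be stated.

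**Conclusion.** The concern holds, and the text is wrong as written. The unit of assignment differs between protocol and SAP, no sibling allocation rule is given, and the two clustering rules conflict in the situation the SAP expects. Under the shared assignment that the SAP presupposes, following the 1.10 rule gives intervals that are modestly too narrow for infant outcomes, the primary one included. If the random-effects sentence is followed instead, they are not narrowed in this way.

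I am confident of the textual conflict. The magnitudes are illustrations that rest on the assumed ICC, twins only, and the assumed attendance inputs. The stated sample size is arithmetically correct for independent neonates, and more neonates are not needed on this account. The point should be fixed before results are seen, because it leaves open the choice of interval for the primary outcome.

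**What to change.** 1. State in protocol sections 4 and 7 whether siblings are assigned together, and make the SAP's definition of the groups match.
2. Replace the 1.10 rule with family-cluster-robust standard errors, or a family random effect, for all infant outcomes including attendance, whatever the mean. One rule then governs.
3. If siblings share an assignment, note beside the sample size that the 80% power assumes independent neonates.
4. If siblings can be split, define the arm for parent-reported outcomes, clarify the survey-packet wording for multiples, and add a sensitivity analysis excluding split families.

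The cost is protocol and SAP wording, with no added patients or data. Under shared assignment with twins only, the intervals become wider by the amounts shown in steps 3 and 4 of the working.

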**8) Data and/or Specimen Management and Confidentiality**

I understand that if this study involves the use of the UC Davis Health Electronic Health Record (EMR/EPIC) also contains the clinical data for Marshall Medical Center (MMC). I understand that MMC patient data cannot be accessed for research purposes and that I must take the necessary steps to ensure that MMC data is not accessed, used, or disclosed for UC Davis Health research purposes.

I understand that if this study involves use of UC Davis students' educational records (including records in the PI's own possession such as course exams/assignments), I must consult with the Registrar's office to see if all requirements of the Family Educational Rights and Privacy Act (FERPA) are satisfied.

**DATA ANALYSIS:** We will analyze subject data according to their assigned group (intervention vs. control). We will use descriptive statistics to summarize subject-level characteristics. We will compare neonatal and parental characteristics between study arms using Pearson's Chi-square test for categorical variables, t-test for normally distributed continuous variables, and nonparametric equality-of-medians test for non-normally distributed continuous variables. Generalized linear models will be used to estimate effect sizes and to test hypotheses for study outcomes, using a binary indicator for intervention assignment as the independent variable of interest and including a parsimonious set of demographic and clinical characteristics as covariates. We will analyze all available data and anticipate high data completion rates, based on our pilot trial. We will conduct sensitivity analyses using multiple imputation approaches for missing data to complement the primary analysis.

**SAMPLE SIZE:** We specified effect sizes of interest for all the trial outcomes and determined the necessary sample size to satisfy each. The sample size estimation that satisfies length of stay requirements also satisfies requirements for all other outcomes of interest, except for medical errors (which are rare and

**PROTOCOL TITLE: Virtual Family-Centered Rounds in the Neonatal Intensive Care Unit:  
A Randomized Clinical Trial**

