thus this outcome will be considered exploratory. Outcome distributional assumptions were based on data from our pilot trial or other relevant literature. Pilot trial baseline mean log transformed length of stay +/- standard deviation (SD) was 3.0 +/- 1.0 days. Minimally clinically important differences (MCID) were based on the literature when available or via consensus opinion elicited from NICU clinicians we consulted. For the length of stay outcome, experts specified that a 25% reduction in geometric mean length of stay was of interest. A randomized sample of 447 neonates (298 intervention, 149 control) subject to 4% attrition in each arm yields a sufficient sample size (429 neonates) to provide 80% power (under two-sided testing, alpha=5%) to detect this MCID. This estimated attrition is based on 4 of 110 randomized subjects in the pilot trial being excluded from final analysis (e.g., child protective visitation restrictions placed after randomization). Parent-reported outcomes assume a survey response rate of 75% (thus n=321 parents). Note: Regarding sample size for the interviews, we anticipate interviewing ~15 parents, ~10 nurses, and ~10 physicians. Consistent with standard qualitative methods, we will continue to sample interview participants until we reach thematic saturation, thus we cannot specify a priori the exact number of interviewees.

All virtual FCR encounters will occur using an application platform that is approved by Information Technology at UC Davis Health System as meeting HIPAA and HITECH data security requirements. The only telehealth communication that will occur will be through the HIPAA-compliant application. No telehealth encounter will be recorded or stored in any way.

Participants will decide to what extent they want to participate in the interviews and surveys. There will be no personal or intrusive questions. In all steps of this pilot study, the risk of loss of confidentiality is very low given the measures described above to protect PHI.

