#### **Methods in analysis to handle protocol non-adherence and any statistical methods to handle missing data**

The primary analysis strategy – a modified intention-to-treat analysis – differs from intention-to-treat only in that it will not require replacing missing data with imputed values. This ‘complete-case’ analysis strategy assumes that missingness is at random. Sensitivity analysis using multiple imputation will be performed to assess the potential impacts of nonignorable missingness and alternative approaches for handling infants whose disposition is not to the home

and thus for whom the outcome may not be as applicable. In particular, for the few infants who transfer to another unit or hospital, the parent-reported outcomes and the 30-day revisit/readmission outcomes are of limited applicability. Our modified intention-to-treat analysis will include these subjects, but alternative analysis that excludes such outcomes from infants not discharged to home would be warranted. We will also estimate alternative treatment effects, such as per-protocol and as-treated.

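### The protocol promises clinical covariates in the outcome models but the SAP's only covariate list names none, leaving two covariate rules and giving up precision on length of stay, the outcome that sized the trial

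*Combined protocol and SAP*

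**What the plan says.** Protocol section 8 (Data analysis) describes generalized linear models for the study outcomes, "including a parsimonious set of demographic and clinical characteristics as covariates". It does not name the covariates.

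The SAP, under *Statistical methods for primary and secondary outcomes*, describes the same class of models with "a parsimonious set of subject characteristics as covariates (parent age, race, ethnicity, gender, education, transportation security", followed by marital status, other dependent children and digital literacy score. The list is not marked as examples, and no separate list is given for neonatal outcomes. On model form the SAP says only: "We will specify the generalized linear mixed models as linear, logistic, or Poisson regressions, according to the outcome type".

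Protocol section 8 (Sample size) makes length of stay the governing outcome, with medical errors the one exception: "The sample size estimation that satisfies length of stay requirements also satisfies requirements for all other outcomes of interest". The inputs are on the log scale ("Pilot trial baseline mean log transformed length of stay", 3.0 with SD 1.0), and "experts specified that a 25% reduction in geometric mean length of stay was of interest".

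Eligibility in section 4 is broad: "Neonates aged <365 days admitted to UC Davis neonatal intensive care unit (NICU) during the study period", with no limit on gestational age or birth weight. The assignment text in section 7 mentions no stratification. The SAP's missing-data section describes a complete-case primary analysis that "differs from intention-to-treat only in that it will not require replacing missing data with imputed values".

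**The concern.** Two rules now govern the same models. An analyst could fit the SAP list with no clinical covariate, or add clinical covariates of their own choosing under the protocol sentence, and cite the documents either way. A SAP should close that choice before outcomes are seen.

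The gap matters most for length of stay. It set the sample size, and its planned power is 80%. If the SAP list governs, no neonatal clinical factor is handled by eligibility, by stratification or by the model. In a linear model, pre-randomization covariates narrow the confidence interval to the extent that they predict the outcome, so leaving them out gives up precision. Growth velocity, listed among the outcomes in section 7 (Data collection), is in the same position, but the documents give it no SD or target effect, so no figure can be worked out. The calculation below does not carry over to the Poisson outcomes (attendance, errors) or the binary ones (such as growth failure).

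**Working it through.** **Inputs from protocol section 8.** 25% reduction in geometric mean, so delta = -ln(0.75) = 0.2877 on the log scale; SD 1.0; two-sided alpha 5%; power 80%; 2:1 allocation; 4% attrition; 447 randomized, 429 analysed.

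**Assumption.** R-squared is the further share of log length-of-stay variance explained by the neonatal covariates. The documents do not give it.

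**Step 1: reproduce the plan's figure.** Control-arm n = (1.960 + 0.842)² × 1.0² × (1 + 1/2) / 0.2877² = 142.3, rounded up to 143. The total is 3 × 143 = 429, and 429 / 0.96 = 446.9, so 447. This matches the plan. For the power check, SE = sqrt(1/286 + 1/143) = 0.1024, noncentrality = 0.2877 / 0.1024 = 2.81, df = 427, and noncentral-t power = 80.03%. The stated power therefore relies on no covariate adjustment.

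**Step 2: add three neonatal covariates.** With k covariate degrees of freedom and N = 429, SE = 0.1024 × sqrt(1 - R²) × sqrt((N - 3)/(N - 3 - k)) and df = N - 2 - k. The middle column uses k = 3 and gives the nine SAP covariates neither degrees of freedom nor explained variance. The right-hand column assumes that the nine use 15 degrees of freedom, so k = 15 before the change and k = 18 after it.

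| Model | Nine not counted | Nine at 15 df (assumed) |
|---|---|---|
| Before the change | 80.03% | 78.6% |
| After, R² = 0 | 79.75% | 78.3% |
| After, R² = 0.05 | 81.7% | 80.3% |
| After, R² = 0.1 | 83.7% | 82.4% |
| After, R² = 0.2 | 87.7% | 86.6% |

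In the middle column the three covariates repay their cost once R² exceeds about 0.007.

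**Step 3: what missing covariates would do.** In a complete-case fit, an infant lacking any covariate is dropped. With k = 3, power returns to 80.03% once about 18 of 429 infants (4.3%) are lost at R² = 0.05, 40 (9.3%) at 0.1, or 82 (19.2%) at 0.2. The documents give no missingness rate for baseline covariates. If 5% of infants lack the neonatal covariates (assumption), complete-case power is 79.7%, 81.8% and 86.0% at those three values. Keeping the infants, with a mean fill over both arms plus a missing indicator, gave 81.4%, 83.6% and 87.5% in simulation (4,000 trials per setting, missingness at random and independent of arm, Monte Carlo SE about 0.6 points).

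The nine parent covariates can also be missing, and the documents do not say how they are collected. If some came only from surveys at the 75% response that section 8 assumes for parent-reported outcomes (assumption), about 321 infants would remain. Power with k = 3 would then be about 70%, 72% and 77% at R² = 0.05, 0.1 and 0.2. A rule that covers only the added neonatal covariates would not prevent this.

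**The case against.** The strongest reply is that nothing here is invalid. The primary outcome is attendance, length of stay is an Aim 2 outcome, randomization protects against bias, and the power claim is right as it stands. All of that is correct, and it is why the point is minor.

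A reader might infer that the SAP has settled on analysing log length of stay with no neonatal baseline factor at all. The documents do not support that, for three reasons. The protocol still promises clinical covariates, so they may be unnamed rather than excluded. The log scale appears only in the sample-size text, so a log-scale linear model is an inference. And the SAP calls its list subject characteristics, where the subject is the neonate, so gender could mean infant sex. The SAP's effect-modifier list speaks of parent race and ethnicity, which favours the parental reading. Even infant sex would add a demographic item and not a clinical one.

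It can also be said that the gain rests wholly on an assumed R-squared and that the documents name neither gestational age nor birth weight. Both are true. The gain is therefore shown as a range, and extraction has to be confirmed first. The mismatch between the two texts needs no assumption.

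Finally, multiple imputation is already planned. It is planned as a sensitivity analysis, so it does not keep infants in the primary complete-case fit.

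**Conclusion.** The protocol and the SAP disagree on whether outcome models carry clinical covariates. Under the SAP list, length of stay would be analysed without any neonatal clinical baseline factor. The consequences are an open analyst choice and forgone precision.

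A reader might go further and conclude that the trial is underpowered or the length-of-stay comparison biased. Neither follows: 447, 429 and 80% reproduce from an unadjusted comparison.

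Leaving the nine existing covariates uncounted, the change in power runs from about -0.3 points if the new covariates explain nothing to +1.7, +3.7 and +7.7 points at R-squared 0.05, 0.1 and 0.2. If the nine use 15 degrees of freedom, the gains at the same three values are +1.7, +3.8 and +8.0 points from a base of 78.6%. These figures assume a linear model on the log scale, SD 1.0, no infants dropped for missing covariates, and an R-squared that the documents do not supply. This is a cheap improvement of minor severity.

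**What to change.** Before outcome data are seen:

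1. Reconcile protocol section 8 with the SAP list. For length of stay and growth velocity at least, add to the SAP a short named set of pre-randomization neonatal covariates, for example gestational age at birth, birth weight and age at NICU admission, entered as linear terms. First confirm that these can be extracted from the EHR.
2. State in the SAP that length of stay is analysed on the log scale, matching the sample-size section.
3. State one missing-value rule for all baseline covariates, including the nine parent or household ones, so that infants are not dropped for a missing covariate under the complete-case strategy. A mean over both arms plus a missing indicator is one option. Say that the rule covers baseline covariates and not outcomes.
4. Keep the protocol's clinical-covariate commitment for the other outcomes, and have the sponsor state whether it applies to each. The calculation here gives no ground for withdrawing it from growth failure or breast milk feeding.

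The cost is SAP wording, an extraction check, about three degrees of freedom plus any used for missing indicators, and about 0.3 points of power if the covariates explain nothing. The sample size does not change.
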